### **3.5.5.1.4 Analysis on the Durability of Vaccine Efficacy**

To evaluate the durability of vaccine efficacy, the incidence of HZ will be summarized by vaccination group and by every 6 months of follow-up post vaccination. A piecewise exponential model will also be carried out to estimate the vaccine efficacy and the corresponding 95% CI by follow-up interval post vaccination. Note that the estimate may be less precise than the overall estimate, due to smaller numbers of events and follow up in time interval. The durability assessment will be conducted for the HM and STM populations separately.

### 3.5.5.1.5 Additional Evaluation of Vaccine Efficacy

To further evaluate the vaccine efficacy for HZ, summaries for the incidence of HZ, secondary composite endpoint and PHN in each vaccination group will also be provided by the following subgroups:

- Disease type and HM immunocompromise category (STM, HM low IC or HM moderate to high IC).
- Gender (male versus female)
- Number of vaccine doses received
- Age categories (< 50 years, 50 to 69, and 70+)

### 3.5.5.2 Analysis of Vaccine Immunogenicity

All immunogenicity analyses are exploratory in this study. The key immunogenicity endpoints include the GMT and the GMFR from prevaccination (Visit 1) at (Day 1 [prior to Dose 1], to Visit 5 [28 to 60 days Postdose 4]) for the VZV antibody titers as measured by gpELISA in all subjects in STM group. A linear mixed longitudinal model will be used on the natural log transformed antibody titers, for the comparison of GMT between 2 vaccination groups across the time points after vaccination. The longitudinal regression analysis model developed by Liang and Zeger [52] will include prevaccination antibody titers and postvaccination antibody titers as response variables. The covariates in the analysis model will include vaccination group, continuous age, visit (indicator for baseline or postvaccination) and vaccination group-by-visit interaction. The antibody titers will be natural-log-transformed in the analyses. The fold-difference between the vaccine and placebo groups and the corresponding 95% CI at the respective visit will be obtained from this model. This analysis will be based on the per-protocol approach. For patients who receive treatments that may interfere with the measurements of VZV-specific antibody response (including those receiving immunoglobulin therapy) or who report an exposure to varicella/HZ within 4 weeks prior to blood draw, or who develop suspected varicella/HZ before the relevant blood sampling, the measurements at corresponding time points and thereafter will be excluded from the gpELISA analysis. The summaries of VZV antibody titers at each time point will also be carried out by vaccine lot at each time point. Patients who receive immunoglobulin therapies will be included in VZV IFN- $\gamma$  ELISPOT analysis as described below.

To evaluate the association between the immune responses and the risk of HZ, a Cox regression model will be used, which will use the immune responses measured by gpELISA at baseline and at 28 days postvaccination dose 4 as covariates. The GMT and GMFR will also be summarized at these time points by vaccination group and HZ outcome (patients who developed confirmed HZ during the study versus those who did not).

In addition, Cox proportional hazards model will be used to estimate the relation between the occurrence of HZ and the gpELISA titers. The gpELISA titers will be used as the covariate to obtain a risk ratio for HZ per unit increase in the titer.

The percent of patients with  $\geq$  2-fold,  $\geq$  3-fold and  $\geq$  4-fold rises in gpELISA at Visit 5 [28 to 60 days Postdose 4] by vaccination group will also be provided.

The proportion of patients achieving seroresponse  $\geq$  400 gpELISA units/mL at Visit 5 [28 to 60 days Postdose 4] will be summarized by vaccination group and by HZ status. A supportive analysis may be provided, including all valid immunogenicity results, regardless of protocol deviations. Patients who reported an exposure to varicella/HZ (if any) will be listed and the corresponding count and proportion will be summarized by vaccination group in the tables regarding the exclusion of patients from the per protocol immunogenicity analyses and a brief description of these patients will be provided in the clinical summary section of the Clinical Study Report.

In addition, direct T cell response to VZV antigen as measured by VZV IFN- $\gamma$  ELISPOT in the ELISPOT substudy participants will be performed at each time point (Day 1 [prior to Dose 1], and Visit 5 [28 to 60 days Postdose 4]). The blood samples will be collected on a subset of  $\sim$ 1000 patients. Similar to gpELISA, VZV IFN- $\gamma$  ELISPOT related summaries and analyses will be considered as exploratory in this study. The same endpoints as for VZV antibody titers measured by gpELISA will be used for GMC as measured by VZV IFN- $\gamma$  ELISPOT. Using the natural log scale of GMC, the analyses will be performed similarly as for gpELISA for the comparison of GMC between 2 vaccination groups and for the evaluation of the association between the GMC and the risk of HZ.

The key immunogenicity measurements will be summarized at each time point (Day 1 [prior to Dose 1], and Visit 5 [28 to 60 days Postdose 4]) by HZ outcome (patients who developed subsequent confirmed HZ during the study versus those who did not) at each time point. It should be noted that VZV IFN- $\gamma$  ELISPOT will be performed in a subset of the study population.

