### **2.7.2 Immunogenicity**

All immunogenicity analyses in this study are exploratory. All patients in the STM study group will have serum samples collected at Day 1/Visit 1 and at Visit 5 (~28 days postvaccination dose 4) to assess a T-cell dependent antibody response by gpELISA. In addition, a subset of study patients (n ~ 1000) in both the STM and HM populations will participate in the ELISPOT substudy and undergo testing for VZV T-cell responses by IFN- $\gamma$  ELISPOT assay. The geometric mean titer (GMT) or geometric mean count (GMC) and geometric mean fold rises (GMFR) for both the gpELISA and ELISPOT will be provided by vaccination group at scheduled time points (see Section 1.7) for the HM and STM populations separately. A longitudinal regression model will be used to estimate the fold difference at these time points between the vaccination groups, while adjusting for the prevaccination titers (see Section 3.5.5.2) for the HM and STM populations separately. Other exploratory analyses will also be performed to determine whether these VZV-specific immune responses are associated with protection against HZ using Cox proportional hazards models in the combined STM and HM populations.

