### **3.5.7.3 Immunogenicity Analysis**

All immunogenicity analyses in this study are exploratory. A subset of patients (n ~ 1000) will participate in the ELISPOT substudy and undergo testing for direct VZV T-cell responses by IFN- $\gamma$  ELISPOT assay. This substudy size is required to adequately power ( $\approx 70\%$ ) the study to detect correlation with efficacy for combined STM and HM population when assuming the true correlation is one unit increase of log scaled post dose 4 ELISPOT GMC will reduce the HZ risk by 18% and standard deviation of log scaled post dose 4 ELISPOT GMC is 2.2 for HM and 1.6 for STM. This substudy size also provides sufficient power ( $>88\%$ ) for each subgroup population for testing fold difference at lower bound of 1.0 when the true fold difference between two groups is 2.0.

In addition, T-cell responses will be indirectly measured using an antibody measure, gpELISA in all patients from STM subgroup. The GMT or GMC and GMFR for gpELISA and ELISPOT will be provided by vaccination group at scheduled time points (see Section 1.7). A longitudinal regression model will be used to estimate the fold difference at these time points between the vaccination groups, while adjusting for the prevaccination titers. Other exploratory analyses will also be performed to determine whether these VZV-specific immune responses are associated with protection against HZ using Cox proportional hazards models.

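### The immunogenicity model listed in 3.5.5.2 leaves baseline means free by arm, so a literal fit does not give the prevaccination-adjusted fold difference stated in 2.7.2 and 3.5.7.3

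*Combined protocol and SAP*

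**What the plan says.** Section 3.5.5.2 specifies a longitudinal model for natural-log gpELISA titers in which the prevaccination and postvaccination values are both responses. On the terms it says: "The covariates in the analysis model will include vaccination group, continuous age, visit (indicator for baseline or postvaccination) and vaccination group-by-visit interaction". On the output it says: "The fold-difference between the vaccine and placebo groups and the corresponding 95% CI at the respective visit will be obtained from this model". The same section states "This analysis will be based on the per-protocol approach". For patients with interfering treatment, exposure or suspected disease, it adds that "the measurements at corresponding time points and thereafter will be excluded from the gpELISA analysis". ELISPOT counts are to be analysed in a similar way.

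Section 2.7.2 describes the fold difference as estimated "between the vaccination groups, while adjusting for the prevaccination titers (see Section 3.5.5.2", so it points to 3.5.5.2 for the adjustment. Section 3.5.7.3 repeats "while adjusting for the prevaccination titers". Section 3.1.2.4 makes the geometric mean fold rise (GMFR) the exploratory objective endpoint for both assays and notes that baseline values appear to affect postvaccination values.

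**The concern.** A two-visit model with group, visit and group-by-visit terms has a free mean for each of the four group-by-visit cells. The group difference at Visit 5 is then estimated without regard to any group difference at Day 1. Adjustment for baseline needs either a common baseline mean in the longitudinal model or the baseline titer as a covariate. Section 3.5.5.2 states neither, and the group main effect it lists is the term that a common-baseline model would omit.

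Two statisticians working from this text could therefore report different estimates. The literal fit has a wider interval and carries any chance baseline imbalance into the Visit 5 contrast, although the plan elsewhere calls that contrast baseline-adjusted. Section 3.5 says no separate SAP will be issued, so 3.5.5.2 is the operative specification.

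**Working it through.** **Inputs from the plan.** ELISPOT: 500 patients per population (2.5.3), randomized 1:1, so 250 per arm. For the SD of the log postdose 4 value, 3.5.7.3 says "GMC is 2.2 for HM and 1.6 for STM". The power target there is "testing fold difference at lower bound of 1.0 when the true fold difference between two groups is 2.0". gpELISA: 1348 per arm (Table 2-1).

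**Assumed, because the plan gives no value.** Pre/post correlation rho of 0.3, 0.5 or 0.7; 20% of patients not evaluable or without a Visit 5 value; gpELISA SD of 0.8 to 1.6; two-sided alpha of 0.05 for the power figure.

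**Step 1: the plan's own power figure.** Power = Phi(ln 2 / (SD × sqrt(2/n)) − 1.96). For HM at 200 per arm: 0.693 / (2.2 × 0.1) − 1.96 = 1.19, giving 88.3%. At 250 per arm HM gives 94.1%. STM gives 99.1% at 200 and 99.8% at 250. The stated figure above 88% is reproduced with the unadjusted SD, so it does not depend on baseline adjustment.

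**Step 2: does the listed model adjust for baseline?** Both models were fitted by generalized least squares to simulated data (250 per arm, SD 1.6, age included). Then 0.3 log units were added to every vaccine-arm baseline value.

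| Change in Visit 5 estimate | rho 0.3 | rho 0.5 | rho 0.7 |
|---|---|---|---|
| As listed | 0 | 0 | 0 |
| Common baseline mean | −0.09 | −0.15 | −0.21 |

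The second row is −0.3 × rho, which is what baseline adjustment does. With 20% of Visit 5 values missing, the as-listed estimate still did not move. Baseline then enters only through the pre/post correlation, and a between-arm imbalance is still not adjusted for.

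**Step 3: precision.** Variance relative to the as-listed Visit 5 contrast:

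| | rho 0.3 | rho 0.5 | rho 0.7 |
|---|---|---|---|
| Adjusted, complete data: 1 − rho² | 0.91 | 0.75 | 0.51 |
| Adjusted, 20% missing: (1 − rho²)/(1 − 0.2 rho²) | 0.93 | 0.79 | 0.57 |
| Ratio of fold rises (group-by-visit term): 2(1 − rho) | 1.4 | 1.0 | 0.6 |

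With complete data the confidence interval for the log fold difference narrows by 5%, 13% and 29%. Simulation (2000 replicates per setting, 250 per arm, SD 1.6) gave constrained-to-listed variance ratios of 0.92, 0.74 and 0.50 with complete data, and 0.93, 0.81 and 0.57 with 20% missing. The ANCOVA ratios were within 0.003 of these.

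**Step 4: 95% intervals at a true fold of 2.0.** Limits = 2.0 × exp(±1.96 × SD × sqrt(2/n) × sqrt(1 − rho²)), with rho = 0 for the as-listed model.

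| | As listed | rho 0.3 | rho 0.5 | rho 0.7 |
|---|---|---|---|---|
| ELISPOT STM, SD 1.6, n = 250 | 1.51–2.65 | 1.53–2.61 | 1.57–2.55 | 1.64–2.44 |
| ELISPOT HM, SD 2.2, n = 250 | 1.36–2.94 | 1.38–2.89 | 1.43–2.79 | 1.52–2.63 |
| gpELISA STM, SD 1.6 assumed, n = 1348 | 1.77–2.26 | 1.78–2.24 | 1.80–2.22 | 1.83–2.18 |

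**Step 5: a one-standard-error chance baseline imbalance.** The as-listed fold difference shifts by exp(rho × SD × sqrt(2/n)) − 1. For ELISPOT this is 4.4%, 7.4% and 10.5% in STM, and 6.1%, 10.3% and 14.8% in HM. For gpELISA it is 0.9%, 1.6% and 2.2% at SD 0.8, and 1.9%, 3.1% and 4.4% at SD 1.6. This is the precision loss of step 3 seen in a single trial, not a further loss.

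**Step 6: a baseline gap in the per-protocol subset.** Assume a gap of 0.1 SD carried to Visit 5 through rho, and a true baseline-conditional fold of 2.0. The as-listed model should then give about 2.0 × exp(rho × 0.1 × 1.6) = 2.10, 2.17 and 2.24. In simulation it averaged 2.11, 2.16 and 2.25. The constrained model and ANCOVA both averaged 2.01, 2.00 and 2.01.

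**The case against.** The strongest reply is that 3.5.5.2 does not rest on the covariate list alone. It names a published longitudinal method, which the reference list describes as one for pre-post designs, and 2.7.2 points to 3.5.5.2 as the place where the adjustment is made. If that method sets the baseline means equal, the three sections agree in intent. This is possible, but it cannot be confirmed from a title, and a reader who fits the listed terms gets the unadjusted contrast. One sentence would settle it.

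Second, the group-by-visit term gives the ratio of GMFRs, which subtracts baseline and serves the endpoint favoured in 3.1.2.4. That is true, so the concern is confined to the fold difference at Visit 5. A change-score contrast is nevertheless a different quantity from the adjusted difference in 2.7.2, and at rho 0.3 its variance is 1.4 times that of no adjustment at all.

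Third, the sizes rest on assumed correlations, and step 6 takes the baseline-conditional fold as the truth, which favours adjustment by construction. Both points stand; the figures show a range, not an expected result.

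Fourth, the set is per-protocol, where free baseline means can be defended, and a common baseline mean fixes the Day 1 fold difference at 1. The first is a real trade-off. The second costs little, because 3.5.5.2 directs the comparison to time points after vaccination.

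Finally, the analysis is exploratory, and Section 3.5 allows changes to exploratory analyses to be explained in the study report. This limits the weight of the point but does not make the sections agree.

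**Conclusion.** The point holds, with minor impact. The model as listed does not show the prevaccination adjustment that 2.7.2 and 3.5.7.3 describe. A literal fit gives up 9% to 49% of the variance of the Visit 5 log fold difference over assumed rho 0.3 to 0.7 with complete data, or 7% to 43% with 20% of Visit 5 values missing. In fold terms the loss is larger for ELISPOT than for gpELISA if the SDs are similar, because each ELISPOT arm is much smaller. No success criterion and no stated power figure depends on it. Confidence is medium, because the cited method may already intend the constraint.

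**What to change.** In 3.5.5.2, choose one of two forms and apply it to both gpELISA and ELISPOT:

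- Keep the longitudinal model, remove the free group main effect, and state that both arms share one baseline mean. The terms become visit, group at the postvaccination visit, and age.
- Use ANCOVA of the Visit 5 log value on the baseline log value, group and age.

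Then make the wording in 2.7.2 and 3.5.7.3 match. In simulation the two forms differed by 0.003 to 0.004 on the log scale on average.

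The first form costs one term removed and one sentence added, plus matching wording in the other two sections. The second also changes the model name in all three sections. Neither needs new data, since baseline samples are already collected.

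The plan should also state the downside. The per-protocol immunogenicity population in 3.5.4.2 applies exclusions after randomization, so a common baseline mean is an added assumption there. ANCOVA avoids that constraint, but randomization does not guarantee an unbiased contrast in that subset under any of these models.

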#### **2.1.4 Exploratory Objectives**

1. To assess the safety and tolerability of V212 when administered to adults with HM.
2. To assess the impact of V212 on the development of HZ in adults with HM.
3. To assess the impact of V212 on the development of moderate to severe HZ-associated pain at any time from HZ onset through the end of the 6 month HZ follow-up period. Moderate to severe HZ-associated pain is defined as 2 or more occurrences of a score of 3 or greater (0-to-10 scale) on the Zoster Brief Pain Inventory (ZBPI) in adults with HM.

4. To assess the impact of V212 on the development of HZ complications defined as the occurrence of any of the following during the study: hospitalization or prolongation of hospitalization due to HZ, disseminated HZ (including disseminated HZ rash or VZV viremia), visceral HZ, ophthalmic HZ, neurological impairment due to HZ, or administration of intravenous acyclovir therapy for treatment of HZ in adults with HM.
5. To assess the impact of V212 on the development of PHN. PHN is defined as a worst pain score (in the previous 24 hours) of 3 or greater (0-to-10 scale) on the ZBPI, that persists or appears greater than or equal to 90 days after the onset of HZ rash in adults with HM.
6. To assess the immunogenicity of V212 in adults with STM or HM.
7. To describe the impact of HZ on activities of daily living (ADL) and quality of life (QoL), and to assess the impact of V212 on interference with ADL and QoL in study patients who develop HZ.
8. To describe HZ-related non-protocol-mandated health care resource utilization (HCRU), and assess the impact of V212 on HZ-related non-protocol-mandated HCRU, and work and productivity loss (WPQ).
9. To assess the impact of V212 on the severity and duration of HZ-related pain.
10. To assess the impact of V212 on the severity of HZ rash including the extent of rash, number of skin lesions present, and number of dermatomes involved.
11. To assess the association of immunogenicity at postvaccination with the risk of HZ in adults with STM or HM.

The exploratory objectives (1)-(5) will be evaluated for HM only; objectives(6)-(10) will be evaluated for STM and HM separately and (11) will be evaluated in both combined STM and HM populations and individual subpopulation.

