### **2.5.3 Immunogenicity Measurements**

The study will provide an exploratory immunogenicity assessment of V212, as shown in Table 2-2. The goal is to assess the immunogenicity of the vaccine and to attempt to demonstrate correlation of immune responses to the vaccine with clinical efficacy. Serum VZV antibody levels will be measured by gpELISA in patients in the STM study group. Serum samples will be collected on Day 1/Visit 1 (prior to Dose 1) and Visit 5 (~28 days Postdose 4) based on the original enrollment plan (~2696 patients).

A subset of the study population will be enrolled in an ELISPOT substudy to measure T cell response by IFN- $\gamma$  ELISPOT. Peripheral blood mononuclear cells (PBMC) will be collected from those enrolled in the ELISPOT substudy (n ~ 1000), on Day 1/Visit 1 (prior to Dose 1) and Visit 5 (~28 days Postdose 4). Participation in the ELISPOT substudy will be limited to select sites based upon accessibility to PBMC processing laboratories. At these sites, the first 500 patients enrolled in the STM group and the first 500 enrolled in the HM group will be enrolled in the ELISPOT substudy.

Patients enrolled in the ELISPOT substudy will have a separate allocation schedule to assure a well-balanced randomization ratio. All investigative sites participating in the ELISPOT substudy will enroll each consented patient into the ELISPOT substudy until the target enrollment of 1000 patients has been met.

Table 2-2

Exploratory Immunogenicity Assessment of V212

Assay	Goal	Population
gpELISA	Assess T cell-dependent antibody response	

• STM = ~2696 patients

• HM = none

IFN- $\gamma$ ELISPOT	Assess T cell response	

• STM = ~500 patients*

• HM = ~500 patients*

\* Limited to select sites with adequate laboratory processing capabilities

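### The exploratory Cox models relating Visit 5 immune response to HZ risk list no vaccination-group term, so a working vaccine biases the expected titer slope toward apparent protection

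*Combined protocol and SAP*

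**What the plan says.** Section 3.5.5.2 sets out two Cox models for gpELISA. The first is one "which will use the immune responses measured by gpELISA at baseline and at 28 days postvaccination dose 4 as covariates". For the second, "The gpELISA titers will be used as the covariate to obtain a risk ratio for HZ per unit increase in the titer". The section then says that ELISPOT will be analysed in a similar way, including "for the evaluation of the association between the GMC and the risk of HZ". Sections 2.7.2 and 3.5.7.3 repeat the plan without adding a group term, stratification by arm or restriction to vaccinees.

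The longitudinal GMT model in the same section does name the arm: "The covariates in the analysis model will include vaccination group, continuous age, visit (indicator for baseline or postvaccination) and vaccination group-by-visit interaction". So does the PHN model in 3.5.5.1.2.

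The aims are stated in three ways. Exploratory objective 11 in 2.1.4 is "To assess the association of immunogenicity at postvaccination with the risk of HZ in adults with STM or HM". Section 2.5.3 wants "to attempt to demonstrate correlation of immune responses to the vaccine with clinical efficacy". Section 2.7.2 says: "Other exploratory analyses will also be performed to determine whether these VZV-specific immune responses are associated with protection against HZ". Section 3.1.2.4 also speaks of potential correlates of V212 efficacy. All immunogenicity analyses are labelled exploratory.

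**The concern.** Vaccination is expected to raise the Visit 5 response and, if it works, to lower HZ risk. In a model fitted to both arms without a group term, patients with high titers are disproportionately vaccinees. The titer slope then mixes two things: the difference between arms, which randomization already explains, and the relation between titer and risk within an arm, which is what a correlate of protection needs. Adding the baseline titer makes the mixing stronger. It removes variation between patients from the Visit 5 titer and leaves a larger share due to arm.

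At stake is the reading of objective 11. A marker that only records who was vaccinated could be reported as associated with protection. Without group in the model, the analyst sees neither the slope within arm nor whether the vaccine effect shrinks once the marker is included.

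**Working it through.** **The plan's own figure.** The only stated figure for a correlate model is about 70% power for ELISPOT in 3.5.7.3. It supposes that "one unit increase of log scaled post dose 4 ELISPOT GMC will reduce the HZ risk by 18" percent (HR 0.82), with log-scale SDs of 2.2 (HM) and 1.6 (STM). Take the design totals as twice the interim triggers in 3.5.1, that is 136 HM and 96 STM cases, and scale them to 500 patients each:

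- D = 500×136/2568 + 500×96/2696 = 26.5 + 17.8 = 44.3 cases.
- Mean variance = (2.2² + 1.6²)/2 = 3.70.
- Power = Φ(|ln 0.82|×√(44.3×3.70) − 1.96) = Φ(0.198×12.80 − 1.96) = 71.9%, with two-sided 0.05 assumed.

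This reproduces the stated figure closely enough.

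**Approximate bias with no within-arm effect.** With 1:1 allocation, the vaccine share of cases is q = (1−VE)/(2−VE). At VE 65%, the value in 3.5.7.1, q = 0.35/1.35 = 0.259, against 0.5 of those at risk. For a 2-fold rise, cases have a lower mean log titer by (0.5 − 0.259)×ln 2 = 0.167. The variance left in the Visit 5 titer after adjustment for baseline (correlation ρ) is V = SD²(1−ρ²) + 0.25(ln 2)², where 0.25(ln 2)² = 0.120. Then ln HR ≈ −0.167/V, z ≈ 0.167×√(D/V), and the chance of nominal p<0.05 ≈ Φ(z − 1.96).

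**gpELISA, two-titer model, 70 cases.** The 70 cases, the SD, ρ and the 2-fold rise are assumptions. The 2-fold figure in 3.5.7.3 is for ELISPOT.

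| SD | ρ | V | HR per log unit | p<0.05 |
|---|---|---|---|---|
| 1.0 | 0.5 | 0.870 | 0.83 | 32% |
| 1.0 | 0.8 | 0.480 | 0.71 | 52% |
| 1.6 | 0.5 | 2.040 | 0.92 | 16% |
| 1.6 | 0.8 | 1.042 | 0.85 | 28% |

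Simulated Cox fits (2000 STM patients, 70 cases) agree: HR 0.83 to 0.71 with 34 to 51% rejection at SD 1.0, and 0.92 to 0.84 with 16 to 31% at SD 1.6. For the titer-only model at SD 1.0, V = 1.120 and HR = exp(−0.167/1.120) = 0.86, with rejection in about 27% of simulated trials. At VE 50% the two-titer rejection rates are about 11 to 28%.

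**Mechanism check.** Further simulations used 2696 STM patients and 90 cases without dropout, and counted only protective results (z < −1.96, nominal 2.5%). At VE 65%, a 2-fold rise and SD 1.0, the two-titer model gave HR 0.81 and 43%. At VE 0 the gpELISA and ELISPOT runs without a group term gave HR 0.99 to 1.00 and 0.5 to 3.3%, so the bias needs a working vaccine.

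**ELISPOT.** With 1000 patients, 44 cases, VE 65% throughout, a 2-fold rise and ρ = 0.5, the two-titer model gave HR 0.93 and 11% falsely protective at SD 1.6, and HR 0.96 and 6% at SD 2.2 (nominal 2.5%). Taking HM efficacy as 0 to 25%, in view of the futility finding, gave HR 0.95 to 0.98 and two-sided rejection of 7 to 10%, against 5%.

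**With group added.** HR returns to 0.99 to 1.01, and rejection to about 5% two-sided (1.5 to 3.5% in the protective direction). ELISPOT variance falls to 3.70 − 0.12 = 3.58, and power to Φ(0.198×√(44.3×3.58) − 1.96) = 70.5%, from 71.9%.

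**The case against.** Several points on the other side stand.

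- The plan does not say that the arms are pooled or that titers are the only terms. It is silent. Pooling is still the natural reading, because no restriction is given and the same section names the arm where it is wanted.
- Objective 11 asks only for association, and a model without group does estimate one. But 2.5.3, 2.7.2 and 3.1.2.4 ask about efficacy and protection, which that slope cannot separate from vaccination itself.
- Section 3.5.5.2 also summarises GMT and GMFR by vaccination group and HZ outcome, and seroresponse by group and HZ status. These give a partial within-arm check, but no adjusted slope.
- The analyses are exploratory, without multiplicity control. They feed no primary, secondary, safety or stopping decision.

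Two stronger readings are tempting. A reader might infer that any marker the vaccine raises will be declared protective. That holds only for the expected hazard ratio: in most of the settings examined, most trials would not reach p<0.05. A reader might also set the gpELISA artefact beside the 18% reduction used to size the ELISPOT substudy. The two are not on a comparable scale. One rests on an assumed gpELISA SD of 1.0 to 1.6, the other on an ELISPOT design with SDs of 1.6 and 2.2.

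**Conclusion.** The point holds as a bias in an exploratory analysis. If V212 works and raises the marker, the models as listed have an expected hazard ratio below 1 for a marker unrelated to HZ within arm.

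For gpELISA the size could matter, but it depends on a fold rise, an SD and a baseline correlation that the documents do not give. The range above is conditional on those assumptions. For ELISPOT, with the documents' own SDs, the effect is small, and a reader should not carry the gpELISA rates over to it. Nothing here touches the primary efficacy analysis.

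**What to change.** In 3.5.5.2, specify the correlate Cox models for gpELISA and ELISPOT with three terms: log Visit 5 response, log baseline response and vaccination group. Report the titer slope within the vaccine group as well. Label any model without group as descriptive association, not evidence of a correlate of protection.

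The cost is a little wording, one covariate and a slightly wider interval on the titer slope, as the small loss of ELISPOT power shows. Section 3.5 allows exploratory analyses to change if the change is listed and explained in the CSR, so no amendment is needed for this alone. Whether follow-up in these models should start at the Visit 5 draw is a separate question, not settled by this argument.

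### The additional gpELISA correlate model is written per unit of titer; it should specify the natural log, because a raw titer can lose power and cannot be set beside the ELISPOT result

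*Combined protocol and SAP*

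**What the plan says.** Section 3.5.5.2 plans two Cox models linking gpELISA to HZ.

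- The first is a model "which will use the immune responses measured by gpELISA at baseline and at 28 days postvaccination dose 4 as covariates". No scale is given.
- The second is introduced as an addition: "The gpELISA titers will be used as the covariate to obtain a risk ratio for HZ per unit increase in the titer". Section 3.3.4 reports the assay in gpELISA units/mL.

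Two other sentences in 3.5.5.2 bear on the scale. In the paragraph on the longitudinal comparison of geometric mean titers, the plan says: "The antibody titers will be natural-log-transformed in the analyses". For ELISPOT it says: "Using the natural log scale of GMC, the analyses will be performed similarly as for gpELISA", and the same sentence goes on to cover the comparison of the vaccination groups "and for the evaluation of the association between the GMC and the risk of HZ".

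Section 3.5.7.3 gives power of about 70% for the ELISPOT correlate only. It assumes that "one unit increase of log scaled post dose 4 ELISPOT GMC will reduce the HZ risk by 18" percent and that the "standard deviation of log scaled post dose 4 ELISPOT GMC is 2.2 for HM and 1.6 for STM". It gives no SD, effect size or power for gpELISA. All immunogenicity analyses are labelled exploratory.

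**The concern.** Elsewhere in its modelling and summaries of immune response, the plan works on log or fold scales: geometric means, fold rises, the longitudinal model, the ELISPOT association and the ELISPOT power assumption. The additional gpELISA Cox model is the one place where the wording points to the raw titer.

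Two things follow if it is programmed as written. First, antibody titers are usually right-skewed, so a few very high values would dominate the slope, and power falls if risk really changes with the log of the titer. Second, a ratio per 1 unit/mL is too close to 1 to read and cannot be compared with a per-log-unit ELISPOT ratio, although section 3.1.2.4 presents the two assays as parallel candidate markers.

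The model serves exploratory objective 11 (section 2.1.4). gpELISA is planned for all of the roughly 2696 STM patients, against about 500 STM patients for ELISPOT (Table 2-2), and STM is now the only target indication. Section 3.5 says that no separate SAP will be issued, so this text is where the scale would be fixed in advance.

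**Working it through.** **1. The plan's own figure.** For a continuous Cox covariate, power = Φ(√(D × SD²) × |ln HR| − 1.96), taking two-sided 0.05 (the plan states no alpha for these models).

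- |ln 0.82| = 0.198.
- SD² averaged over the two populations: (2.2² + 1.6²)/2 = 3.70.
- D is not stated. Appendix 6.3 gives 174 cases as 75% of the combined target, so 174/0.75 = 232 cases among 5264 patients. Prorated to the substudy ("A subset of patients (n ~ 1000) will participate in the ELISPOT substudy"), D = 232 × 1000/5264 = 44.1.

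Power = Φ(√(44.1 × 3.70) × 0.198 − 1.96) = Φ(0.574) = 71.7%, against the stated 70%. The figure therefore reproduces with a log-scale ELISPOT covariate. The gpELISA scale does not enter it.

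**2. Information lost by a raw covariate.** For a log-normal titer with ln SD s and a log-linear hazard, the local efficiency of raw against log is s²/(exp(s²) − 1). At s = 1.0 this is 1/(2.718 − 1) = 0.582, a loss of 42% of the effective events.

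**3. Power lost.** Simulated Cox fits used 3000 runs per setting, 2696 STM patients, 90 cases (section 3.5.7.1), HR 0.82 per ln unit and two-sided 0.05, with no adjustment for vaccination group or baseline. The HR is borrowed from ELISPOT, and every SD is an assumption. LRT is the likelihood-ratio test. Wald losses are relative to the log-scale Wald power.

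| ln SD | Power, log | Power, raw (Wald) | Power, raw (LRT) | Relative loss, Wald | Relative loss, LRT | Information loss |
|---|---|---|---|---|---|---|
| 0.5 | 16% | 13% | 15% | 17% | 6% | 12% |
| 0.8 | 32% | 22% | 28% | 33% | 11% | 29% |
| 1.0 | 48% | 26% | 36% | 45% | 24% | 42% |
| 1.2 | 62% | 30% | 45% | 51% | 27% | 55% |
| 1.5 | 82% | 34% | 54% | 58% | 34% | 73% |
| 1.6 | 85% | 35% | 55% | 59% | 36% | 79% |

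With the effect instead set to give 80% power on the log scale, the relative loss over the same SDs is 8-63% (Wald) or 4-37% (LRT).

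Cases before Visit 5 cannot inform a postdose 4 correlate. With 80 cases (600 runs) and HR 0.82, power on the log scale is 44% at SD 1.0 and 76% at SD 1.5. On the raw scale it is 24% and 29% by Wald, or 33% and 49% by LRT. Power falls on both scales and the relative loss is similar.

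**4. Size of a per-unit ratio.** Take the 400 units/mL seroresponse threshold in 3.5.5.2 and HR 0.82 per ln unit. A doubling to 800 gives 0.82^(ln 2) = 0.87. Spread over 400 units this is 0.87^(1/400) = 0.9997 per unit, which prints as 1.00.

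**The case against.** The strongest reply is that the log was intended throughout. The longitudinal paragraph has already said that its titers are natural-log transformed, so the later general sentence on log transformation is redundant unless it reaches further, and it speaks of analyses in the plural. The ELISPOT sentence puts the HZ association on the natural log scale and calls that similar to gpELISA. On this reading, a unit of titer means a unit of log titer.

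This part stands: the scale is unclear, and a reader who infers that the plan has firmly chosen the raw titer goes too far. It does not remove the point. The log sentence lies between the longitudinal model's covariates and that model's fold-difference. The Cox sentence comes later, is more specific and speaks of the titer itself. Two programmers could defensibly produce different analyses.

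Three further replies also have force. The log-linear hazard used in the simulation is an assumption that favors the log scale, and the documents do not establish it. The near-1.00 ratio is partly a matter of units: reporting per 100 units/mL would change no test, though it would still not match the ELISPOT scale. The objective also does not rest on this model alone, since the plan includes the first Cox model, geometric means and fold rises by HZ outcome, and seroresponse by HZ status. Section 3.5 allows exploratory analyses to change with an explanation in the study report, but choosing the scale after unblinding would make the correlate result data-dependent.

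**Conclusion.** The point holds as a small correction to an exploratory analysis. Read literally, the additional gpELISA Cox model uses the raw titer, out of line with the plan's log-scale treatment of both markers elsewhere, and the first gpELISA Cox model has no stated scale.

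If titers are roughly log-normal and risk is log-linear, the raw scale costs power: about 17-59% in relative terms by Wald test, or 6-36% by LRT, at HR 0.82 per ln unit and 90 cases for ln SD 0.5-1.6. At the low end the difference is slight (16% against 13-15%).

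A reader might infer a flat loss of 40-70%. The documents do not support that. They give no gpELISA SD or effect size, and that range fits the loss of information at an SD of about 1.0-1.5 (42-73%) rather than the loss of power, which also depends on the test. Nor does the point touch the stated 70%: that is an ELISPOT figure, already on the log scale. No primary or secondary conclusion is affected.

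**What to change.** Add one sentence to 3.5.5.2: baseline and Visit 5 gpELISA titers enter both Cox models as natural logs, and the hazard ratio is reported per ln unit or per 2-fold increase, on the same scale as ELISPOT. Replace the wording that refers to a unit of titer.

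The change needs no new data, leaves the primary and secondary analyses alone and, if the log was always intended, only records that. It should be made before the database is unblinded.
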